### **1.2.2 R-ICE for relapsed and refractory B cell lymphoma**

As R-ICE has been compared to R-DHAP in the salvage setting without demonstrable difference in response rates as mentioned above, R-DHAP was associated with significantly more grade 3 to 4 hematologic and non-hematologic toxicity. Most notably, 6% grade 4 nephrotoxicity was seen in the R-DHAP group compared to 1% in the ICE group. This is attributable to the nephrotoxicity of cisplatin in the R-DHAP regimen. This nephrotoxicity can have critical implications to further therapy; including allogeneic stem cell transplantation wherein the use of potentially nephrotoxic calcineurin-inhibitor based graft-versus-host disease prophylaxis may be contraindicated. Perhaps more importantly, the Bio-CORAL correlative study suggested a potential signal of improved chemosensitivity with R-ICE compared to R-DHAP in ABC-subtype rel/ref DLBCL by gene expression profiling. This provides clear rationale for selectively studying R-ICE in ABC-subtype rel/ref DLBCL in combination with the selective BTK inhibitor ibrutinib.

### *Efficacy*

Of the 20 patients evaluable for a response, 11 achieved a CR and 7 achieved a PR for an overall response rate of 90%. By ITT, 8/9 patients with non-GC DLBCL achieved a CR (89%), with one aforementioned patient removed from study for toxicity (grade 3 atrial fibrillation). Thus, all 8 patients with non-GC DLBCL that completed 3 cycles of therapy achieved a complete metabolic remission. Additionally, all 5 patients with rel/ref Richter's transformed CLL/SLL achieved a response (CR=2, PR=3). In univariate analysis, rel/ref non-GC DLBCL demonstrated a significantly increased rate of CR compared to other subtypes ( $p = 0.008$ ).

At a median follow-up of 14 months for survivors, the one-year event-free (EFS), progression-free (PFS) and overall survival (OS) by ITT was 0.51 (95% CI: 0.33-0.79), 0.62 (95% CI: 0.43-0.9) and 0.65 (95% CI: 0.46-0.93), respectively. Of the 18 patients that achieved a response on study,  $n=14$  and  $n=2$  proceeded to HDT-ASCT and allogeneic hematopoietic transplantation (allo-HCT), respectively. The one-year PFS and OS of transplanted patients on study are 0.73 (95% CI: 0.51-0.99) and 0.82 (95% CI: 0.62-0.99), respectively.

## **1.3 ACALABRUTINIB (ACP-196)**

Acalabrutinib is an imidazopyrazine analogue with a molecular weight of 465.5 g/mol. The compound has 1 stereogenic center and acalabrutinib is the S-enantiomer. Acalabrutinib is orally bioavailable in humans and is suitable for formulating in capsules. Acalabrutinib is approved in the US for the treatment of adult patients with MCL who have received at least 1 prior therapy. It is also being evaluated for the treatment of patients with other B-cell malignancies.

### **1.3.1 Mechanism of Action**

Acalabrutinib is a potent inhibitor of BTK in vitro and in vivo. Pharmacology models have been used to define kinase selectivity of acalabrutinib in comparison to other BTK inhibitors, and to investigate functional effects of on-target and off-target activities. Acalabrutinib shows improved selectivity for BTK compared with ibrutinib. Functional inhibition of non-target cells (eg, T cells, NK cells, platelets) was not observed for acalabrutinib at clinically relevant concentrations.

In [Table 1-1](#) the group of 3F-Cys kinases are listed with the  $IC_{50}$  for acalabrutinib and ibrutinib. For acalabrutinib, the strongest inhibition was observed for Btk with less activity against Tec, Bmx, and ErbB4. However, ibrutinib showed inhibition of all 10 kinases. One kinase potently inhibited by ibrutinib is EGFR, which may explain the ibrutinib-related incidence of diarrhea and rash reported for ibrutinib in clinical trials of hematologic malignancies ([IMBRUVICA prescribing information](#)).

**Table 1-1. Potency of acalabrutinib and Ibrutinib on Group of 3F-Cys Kinases**

	IC 50 (nM)	
	Acalabrutinib 	Ibrutinib 
Btk	3.1	0.5
Tec	29	78
Bmx	39	0.80
Itk	>1000	10.7
Txk	291	2.0 
EGFR	>1000	5.6
ErbB2	912	9.4
ErbB4	13.2	2.7 
Blk	>1000	0.5
Jak3	>1000	16.1

IC50 = inhibitory concentration causing half-maximal inhibition

Profiling at Life Technology

[Honigberg 2010](#); ibrutinib data for Txk and ErbB4 profiled at Life Technology

### 1.3.2 Safety Pharmacology

In vitro and in vivo safety pharmacology studies with acalabrutinib have demonstrated a favorable nonclinical safety profile; for detailed information on the safety pharmacology of acalabrutinib, refer to the Investigator Brochure.

### 1.3.3 Drug-drug Interaction Potential

For more detailed information on drug-drug interaction potential for acalabrutinib, refer to the Investigator Brochure.

Please refer to [Section 3.9.2](#) for guidance on drugs that may cause drug-drug interactions.

## 1.4 CLINICAL EXPERIENCE – ACALABRUTINIB

For more detailed information on the clinical experience for acalabrutinib, please refer to the Investigator Brochure.

### 1.4.1 Clinical Efficacy –

In study LY-002, a phase Ib study of single-agent acalabrutinib for B cell lymphomas, in non-GCB DLBCL (by IHC), n=21, responders n = 5 (24%, 3 ABC, 1 GCB, and 1 indetermined by NanoString). The CR rate was 19%. The ORR for patients with ABC-subtype (non-GCB) by NanoString was 33% (3/9) with 22% (2/9) achieving a CR. The most common  $\geq$  grade 3 adverse event was anemia. Median steady-state BTK target occupancy was 97-99% in 5 patients analyzed at acalabrutinib 100 mg orally twice-daily. (Dyer et al ASCO Annual Meeting 2018 abstract #7547).

This section briefly summarizes data from ACE-CL-001 (NCT02029443), an ongoing non-randomized, sequential group, dose-escalation Phase 1/2 study in subjects with relapsed/refractory or previously untreated chronic lymphocytic leukemia (CLL), Richter's syndrome, or prolymphocytic leukemia.

Acalabrutinib has been well tolerated at all dose levels evaluated. No DLTs have occurred at any dose level. The MTD was not reached in this study, and the dose escalation was stopped at 400 mg.

Preliminary Day 1 PK data revealed variable and dose-linear PK. There was no accumulation of acalabrutinib in plasma upon repeat dosing. For detailed information on the safety and PK of acalabrutinib, refer to the Investigator Brochure.

Preliminary PD data from ACE-CL-001 show that Btk occupancy with acalabrutinib, in peripheral blood cells, is  $\geq$  90% at 4 hours after dosing but declines over 24 hours with QD dosing, while with 100 mg BID dosing, full Btk occupancy (94% to 97%) is maintained over 24 hours. These data suggest that synthesis of de novo Btk may occur within 24 hours.

## **1.4.2 Adverse Events –**

Safety analysis of acalabrutinib monotherapy was conducted to assess safety for acalabrutinib-exposed subjects with hematologic malignancies without confounding toxicity from combination therapy drugs. Overall, the safety of monotherapy acalabrutinib in subjects with hematologic malignancies has been acceptable in the integrated analysis – refer to section 6.3.1 of the Investigator Brochure 9.0.

### **1.4.2.1 *Hemorrhage***

Serious hemorrhagic events, including fatal events, have occurred in clinical studies with acalabrutinib (see [Table 24 of the Investigator's Brochure](#)).

The mechanism for hemorrhage is not well understood. Patients receiving antithrombic agents may be at increased risk of hemorrhage. Use caution with antithrombotic agents and consider additional monitoring for signs of bleeding when concomitant use is medically necessary.

Consider the benefit-risk of withholding acalabrutinib for at least 3 days pre- and post-surgery.

Subjects with hemorrhage should be managed per institutional guidelines with supportive care and diagnostic evaluations as clinically indicated.

### **1.4.2.2 *Infection***

Serious infections (bacterial, viral, and fungal) including fatal events, have occurred in clinical studies with acalabrutinib. The most frequently reported Grade  $\geq 3$  infection was pneumonia (preferred term). Across the acalabrutinib clinical development program (including subjects treated with acalabrutinib in combination with other drugs), cases of hepatitis B virus reactivation, aspergillosis, and progressive multifocal leukoencephalopathy (PML) have occurred (see [Table 24 of the Investigator's Brochure](#)).

Consider prophylaxis in patients who are at increased risk for opportunistic infections. Subjects should be monitored for signs and symptoms of infection and treated as medically appropriate. Subjects with infection events should be managed according to institutional guidelines with maximal supportive care and diagnostic evaluations as clinically indicated.

### **1.4.2.3 *Cytopenias***

Grade 3 or 4 cytopenias including neutropenia, anemia, and thrombocytopenia have occurred in clinical studies with acalabrutinib. Monitor blood counts as medically appropriate (see [Table 24 of the Investigator's Brochure](#)).

Subjects with cytopenias should be managed according to institutional guidelines with maximal supportive care and diagnostic evaluations as clinically indicated. Subjects should be closely monitored as appropriate.

### **1.4.2.4 *Second Primary Malignancies***

Events of second primary malignancies, including non-skin carcinomas, have occurred in clinical studies with acalabrutinib. The most frequently reported second primary malignancy was skin cancer (see [Table 24 of the Investigator's Brochure](#)).

Subjects should be monitored for signs and symptoms of malignancy. Subjects who develop a second primary malignancy should be managed according to institutional guidelines with diagnostic evaluations as clinically indicated, and it may be necessary for subjects to permanently discontinue study treatment. Continuation of acalabrutinib treatment should be discussed with the medical monitor.

#### **1.4.2.5 Atrial Fibrillation**

Events of atrial fibrillation/flutter have occurred in clinical studies with acalabrutinib, particularly in subjects with cardiac risk factors, hypertension, diabetes mellitus, acute infections, or a previous history of atrial fibrillation (see [Table 24 of the Investigator's Brochure](#)).

Monitor for symptoms of atrial fibrillation and atrial flutter (e.g., palpitations, dizziness, syncope, chest pain, dyspnea) and obtain an ECG as clinically indicated. Subjects with atrial fibrillation should be managed per institutional guidelines with supportive care and diagnostic evaluations as clinically indicated.

### **1.5 R-ICE**

R-ICE is one of the most common implemented salvage chemotherapy for r/r DLBCL with CR rate of 63.5%. Hematologic toxicity is universal with 57% of patients requiring transfusion of blood products. Grade 3 and 4 toxicities include neutropenic fever and infections. Subjects should be closely monitored for infection and need for blood products. As describe on section 3.6 all subjects included in the study will require G-CSF on day 5 after chemotherapy.

## **2 STUDY OBJECTIVES**

### **2.1 PRIMARY OBJECTIVE:**

The primary objective is to improve CR rate of R-ICE for rel/ref non-GC DLBCL from 29% to 50% with acalabrutinib + R-ICE for 3 cycles by RECIL.

### **2.2 SECONDARY OBJECTIVE(S):**

- Safety and tolerability of acalabrutinib with R-ICE in patients with rel/ref DLBCL
- PR, CR, ORR of acalabrutinib + R-ICE
- Ability to mobilize  $> 2 \times 10^6$  CD34+ cells/kg
- EFS, PFS and OS at 1 year

[figure not shown]
### **2.3 EXPLORATORY OBJECTIVE(S)**

Correlate efficacy endpoints (ORR, PFS, OS) with: baseline metabolic tumor volume (MTV), circulating cell-free tumor DNA (ctDNA), and the results of next-generation sequencing (NGS) of tumor. NGS in diagnostic biopsy if available.

## **3 STUDY DESIGN**

This is a multi-center, open-label, single arm phase II study of acalabrutinib in combination with R-ICE in rel/ref non-GC DLBCL per Hans criteria, transformed CLL/SLL (tCLL/SLL) and transformed marginal zone lymphoma (MZL). Please see schema below.

The study schema is provided below ([Figure 3-1](#)).

**Figure 3-1. Study Schema**

### 3.1 STUDY PARAMETERS

#### 3.1.1 Efficacy Parameters

EFS, PFS, OS

PFS is defined as the time from start of study entry until disease progression or death. EFS is measured from the time from study entry to the event. Events are defined by: progression of disease, death, or removal from study for any reason. OS is defined as the time from study entry or initial diagnosis until death from any cause.

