### 3.3 SELECTION OF STUDY POPULATION

#### 3.3.1 Inclusion Criteria

Eligible subjects will be considered for inclusion in this study if they meet **all** of the following criteria:

1. Men and women  $\geq$  18 years of age.
2. Patients must have histologic confirmation of relapsed or refractory lymphoma.
3. Baseline FDG-PET scans must demonstrate positive lesions compatible with CT defined anatomical tumor sites.
  - a) CT scan showing at least:
    - i) 2 or more clearly demarcated lesions/nodes with a long axis  $>1.5\text{cm}$  and short axis  $\geq 1.0\text{cm}$ , or
    - ii) 1 clearly demarcated lesion/node with a long axis  $>2.0\text{cm}$  and short axis  $\geq 1.0\text{cm}$ .
4. Patient must have been previously treated for B cell non-Hodgkin lymphoma with any of the allowable below:
  - a) First-line treatment with rituximab and an anthracycline-based chemotherapy.
  - b) Monotherapy rituximab, dosed prior to first-line rituximab combined with anthracycline containing chemotherapy, or as maintenance therapy.
  - c) Radiotherapy as part of the first-line treatment plan including anthracycline and rituximab.
5. Eastern Cooperative Oncology Group (ECOG) performance status of 0 to 2 (See Appendix 2)
6. Life expectancy of greater than 6 weeks.
7. Patients must have normal organ and marrow function as defined below,
  - a) absolute neutrophil count  $\geq 1000/\text{mcL}$  (unless due to lymphoma involvement of the bone marrow)
  - b) platelets  $\geq 75,000/\text{mcL}$  (unless due to lymphoma involvement of the bone marrow)
  - c) total bilirubin  $<1.5 \times$  within normal institutional limits (unless due to lymphoma involvement of liver or a known history of Gilbert's disease)
  - d) AST(SGOT)/ALT(SGPT)  $\leq 2.5 \times$  institutional upper limit of normal (unless due to lymphoma involvement of liver)
  - e) creatinine within normal institutional limits, or
  - f) creatinine clearance  $\geq 40 \text{ mL/min}/1.73 \text{ m}^2$  for patients with creatinine levels above institutional normal. (unless due to lymphoma)
8. Major surgical procedure within 28 days of first dose of study drug. If a subject had major surgery, they must have recovered adequately from any toxicity and/or complications from the intervention before the first dose of study drug.
9. Women who are sexually active and can bear children must agree to use highly effective forms of contraception during the study and for 90 days after the last dose of acalabrutinib + R-ICE.

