#### 3.3.2 Exclusion Criteria

Subjects will be ineligible for this study if they meet **any** of the following criteria:

1. Germinal-center cell-of-origin DLBCL

2. Patients who have had chemotherapy or radiotherapy < 21 days prior to first administration of study treatment or those who have not recovered from adverse events due to agents administered more than 4 weeks earlier.
3. Patients who are receiving any other investigational agents.
4. Patients with known central nervous system involvement of lymphoma.
5. History of allergic reactions attributed to compounds of similar chemical or biologic composition to acalabrutinib or R-ICE with the exception of first-infusion reaction to rituximab.
6. Uncontrolled intercurrent illness including, but not limited to, ongoing or active infection, symptomatic congestive heart failure, unstable angina pectoris, cardiac arrhythmia, or psychiatric illness/social situations that would limit compliance with study requirements. Recent infections requiring systemic treatment need to have completed therapy > 7 days before the first dose of study drug.
7. Pregnant women are excluded from this study because an acalabrutinib R-ICE is a chemotherapy program with the potential for teratogenic or abortifacient effects. Because there is an unknown but potential risk for adverse events in nursing infants secondary to treatment of the mother with acalabrutinib R-ICE, breastfeeding should be discontinued if the mother is treated with acalabrutinib R-ICE.
8. HIV-positive patients on combination antiretroviral therapy are eligible, unless the patient's CD4 count is below the institutional lower limit of normal, or the patient is taking prohibited CYP3A4/5 strong inhibitors or inducers.
9. Patients may not have received any anti-cancer therapy for their primary rel/ref DLBCL with the exception of palliative RT.
10. Uncontrolled Autoimmune Hemolytic Anemia or ITP resulting in (or as evidenced by) declining platelet or Hgb levels within the 4 weeks prior to first dose of study drug.
11. Presence of transfusion-dependent thrombocytopenia.
12. Prior exposure to a BTK inhibitor.
13. History of prior malignancy, with the exception of the following:
  - a) Malignancy treated with curative intent felt to be at low risk for recurrence by treating physician
  - b) Adequately treated non-melanomatous skin cancer or lentigo maligna melanoma without current evidence of disease

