#### **4.1.2 Medical History**

Collect and record the subject's complete history through review of medical records and by interview. Concurrent medical signs and symptoms must be documented to establish baseline severities. A disease history, including the date of initial diagnosis and list of all prior anticancer treatments, and responses and duration of response to these treatments, also will be recorded.

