#### **4.1.5 Confirmation of Eligibility**

Subject eligibility for enrollment will be assessed per [Section 3.3](#). All screening procedures, unless otherwise indicated, should be completed within 28 days of the first dose of study drug.

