### **5.2.4 Analysis of Efficacy Parameters**

Analysis of efficacy parameters will be evaluated using the efficacy parameters defined in section 3.1.1 using the RECIL response criteria outlined in 4.1.16.

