### **5.2.6 Secondary Efficacy Endpoint**

ORR and PR rates will be calculated along with exact 95% CIs based on binomial distribution. PFS is defined as the time from first dose to documented disease progression, or death from any cause, whichever occurs first. Data for subjects who are still alive and free from progression at the time of data cutoff date, lost to follow-up, or have discontinued the study will be censored on last assessment (or, if no post-baseline tumor assessment, at the time of first dose plus 1 day). Duration of PFS will be estimated using Kaplan-Meier methodology.

Approximate 95% CIs for median duration of PFS will be computed using the formula proposed by Brookmeyer and Crowley.

EFS is defined as the time from first dose to documented disease progression, death from any cause, or study dropout, whichever occurs first. Duration of EFS will be estimated using Kaplan-Meier methodology. Approximate 95% CIs for median duration of EFS will be computed using the formula proposed by Brookmeyer and Crowley.

OS is defined as the time from first dose to death from any cause. Data for subjects who are still alive at the time of data cutoff date, lost to follow-up, have discontinued the study (or, if no post-baseline assessment, at the time of first dose plus 1 day) will be censored. Duration of OS will be estimated using Kaplan-Meier methodology. Approximate 95% CIs for median duration of OS will be computed using the formula proposed by Brookmeyer and Crowley.

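### Overall survival has three possible start dates and no rule for choosing between them; one of them, initial diagnosis, would count survival that eligibility guarantees

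*Combined protocol and SAP*

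**What the plan says.** Section 3.1.1 (Efficacy Parameters): "OS is defined as the time from study entry or initial diagnosis until death from any cause". The same section starts PFS and EFS at study entry, and its EFS events are progression, death, or being taken off the study for whatever reason.

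Section 5.2.6 (Secondary Efficacy Endpoint): "OS is defined as the time from first dose to death from any cause". PFS and EFS also start at first dose there, and the third EFS event is dropout from the study. Neither study entry nor dropout is defined.

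Section 5.2.4, which sits between the two in the reader's path, says "Analysis of efficacy parameters will be evaluated using the efficacy parameters defined in section 3.1.1". No section states which definition prevails. Section 5.2.1 lists PFS, EFS and OS at 1 year as secondary endpoints.

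Three other provisions bear on the diagnosis origin:
- Section 3.3.1 requires relapsed or refractory disease after earlier treatment, for example "First-line treatment with rituximab and an anthracycline-based chemotherapy".
- Section 3.3.2 excludes chemotherapy or radiotherapy given less than "21 days prior to first administration of study treatment".
- Section 4.1.2 collects "A disease history, including the date of initial diagnosis and list of all prior anticancer treatments", so the diagnosis clock can actually be run.

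**The concern.** No patient can enter without having survived diagnosis, first-line treatment and relapse or refractoriness. If OS is counted from diagnosis without adjustment for that delayed entry, the early part of the curve is free of deaths by construction. A patient diagnosed a year or more before entry is alive at 1 year whatever the regimen does. For the transformed CLL/SLL and marginal zone patients admitted under section 3, the text also leaves open whether the initial diagnosis is that of the indolent disease or of the transformation.

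The other differences are of the same kind but smaller. The choice between study entry and first dose shifts all three curves a little, and it affects whether an enrolled but never-dosed patient has a time zero. The two EFS lists can disagree on a patient whom the clinician takes off study without progression.

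In an open-label, single-arm trial, these choices should not remain open until results are known.

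**Working it through.** **1. The two sections side by side**

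| Item | Section 3.1.1 | Section 5.2.6 |
|---|---|---|
| OS origin | study entry, or initial diagnosis | first dose |
| PFS origin | study entry | first dose |
| EFS origin | study entry | first dose |
| EFS events | progression, death, any removal from the study | progression, death, dropout from the study |

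The plan gives no target, event count or power for OS, PFS or EFS, so there is no figure of its own to reproduce. The calculations below only show size.

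**2. Diagnosis clock for OS**

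Inputs: 1-year OS of 0.65 from the phase I ibrutinib + R-ICE trial (section 1.2.3, Efficacy), used here as if it ran from first dose; constant hazard (assumed); and a gap of g months from diagnosis to first dose, the same for every patient. The documents give no gap. They support only a floor of 21 days, for patients who had first-line chemotherapy (section 3.3.2).

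Nobody can die during the gap, so only 12 − g months are at risk: OS at 12 months = 0.65^((12 − g)/12), and 1 if g is 12 or more.

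- 21-day floor: 0.65^((365 − 21)/365) = 0.666
- g = 3 (assumed): 0.65^0.75 = 0.724
- g = 6 (assumed): 0.65^0.5 = 0.806
- g ≥ 12 (assumed): 1.000

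With a base of 0.50, gaps of 3, 6 and 12 months give 0.595, 0.707 and 1.00. With a base of 0.75 they give 0.806, 0.866 and 1.00.

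For scale, the approximate 95% half-width at n = 46 is 1.96 × √(0.65 × 0.35/46) = 0.138. The floor moves the estimate by 1.6 points, well inside that. A 6-month gap moves it by 15.6 points, which is outside.

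**3. Study entry versus first dose**

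Inputs: phase I 1-year OS 0.65, PFS 0.62 and EFS 0.51 (section 1.2.3), and d days from entry to first dose. Section 4.1.5 gives an upper figure: "All screening procedures, unless otherwise indicated, should be completed within 28 days of the first dose of study drug". The 7-day value is assumed.

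Formula: S^((365 − d)/365).

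- d = 7: OS 0.655, PFS 0.626, EFS 0.517 (shifts of 0.5 to 0.7 points)
- d = 28: OS 0.672, PFS 0.643, EFS 0.537 (shifts of 2.2 to 2.7 points)

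The 28-day case needs study entry to mean the start of screening and every patient to use the whole window.

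**4. EFS event list**

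Section 1.2.3 describes one phase I patient, of 21, who was removed after cycle 2 for an asymptomatic imaging finding while in CR, went on to transplant and was reported as remaining progression-free. That patient is an event under the 3.1.1 list and may not be under the 5.2.6 list. Effect on crude EFS: 1/21 = 4.8 points. The same share of 46 patients is 46/21 = 2.2 patients. If such a patient stops treatment but stays on study, as section 3.4.1 allows, the lists agree and the effect is zero.

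**The case against.** The strongest reply is that section 5.2.6 is the working definition. It is the only text with censoring rules, and it sets its fallback censoring time at one day after first dose, which makes no sense on a diagnosis clock. One-year endpoints with 52 weeks of follow-up after end of treatment also fit a treatment or entry origin. This stands in part: it makes the diagnosis clock the less likely reading. It does not remove the conflict, because section 5.2.4 directs the analysis to 3.1.1 and the diagnosis date is collected.

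It is also fair that every gap above 21 days is assumed. Section 1.2.3 does not state the time origin of the 0.65, and that trial used a different BTK inhibitor in all cells of origin.

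Three stronger readings are tempting and are not supported:

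- **That 1-year OS will be inflated by 15 points or more.** This needs both the less likely reading and an assumed gap.
- **That the EFS lists differ by 2/21 = 9.5 points.** This adds the phase I patient removed by physician decision after atrial fibrillation. That patient's later course is not reported; had progression or death followed within the year, both lists would show an event by 1 year.
- **That patients who progress are censored for OS, biasing it upward.** Section 4.2 and Appendix 1 footnote h do speak of removal from study at progression, and 5.2.6 censors those who discontinue the study. But the synopsis refers to removal from study treatment, section 3.4.1 separates stopping treatment from leaving the study, and section 4.4 places progressors in survival follow-up. Their deaths most likely count.

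**Conclusion.** The point holds as a defect in the definitions. Section 3.1.1 names an OS origin that is wrong for a relapsed or refractory population, 5.2.6 names a different one, and no precedence is stated. If the diagnosis clock were used, 1-year OS would be too high. On a base of 0.65 with constant hazard, the rise runs from about 2 points at the only gap the documents support to 35 points at an assumed gap of a year or more. Use of that clock is possible, not expected.

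The entry-versus-first-dose difference is under 1 point at an assumed 7 days and about 2 to 3 points at most. The EFS list difference is 4.8 points on the single documented case and may be nil. No bias from OS censoring is claimed.

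These endpoints are secondary and estimated without a test, and the two-stage CR rule is untouched. The matter should be fixed before analysis, but it does not threaten the primary conclusion.

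**What to change.** - In section 3.1.1, delete initial diagnosis as an OS origin.
- Use one origin for OS, PFS and EFS in 3.1.1 and 5.2.6. First dose is the natural choice because 5.2.6 already uses it, and it sits well with section 3.4.4, under which enrolled but untreated subjects may be replaced. Study entry would also remove the bias, provided it is defined and used in both places.
- Put the same EFS event list in both sections, and say whether removal by the clinician without progression is an event.
- As wording clean-up only, reconcile the statements on removal at progression in section 4.2 and Appendix 1 footnote h with the synopsis and sections 3.4.1 and 4.4.

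The cost is a few sentences in an amendment. First-dose date and survival status are already collected, and neither the sample size nor the visit schedule changes.
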